Thoracic kyphosis will be measured using two gravity dependent inclinometers (Isomed Inc.). Spinal processes will be determined by palpation by a registered nurse or pediatric nurse practitioner. The feet of the inclinometers will be placed over the spinal processes thought to be at T1, T2 and T12, L1. The measurements will be taken in relaxed standing and measured 3 times in succession. Clinical assessment of the thoracic kyphosis angle is considered essential in postural examination, but can be time

consuming when measured radiographically (Lewis, 2010). Lewis and Valentine studied intra-rater reliability in subjects with and without symptoms and found measurements of less than 1.7 degrees should be considered measurement error. The test-re-test reliability established excellent intra-rater reliability. Although validity of this measure is less studied, the measurement is thought to provide guidance of how much change of the kyphoscoliosis angle is a real consequence of intervention over time (Lewis, 2010).

5. Patient/Family Surveys

A brief ten minute written survey will be administered to subjects to ascertain level of satisfaction with the program.

B. Description of Population to be Enrolled: Study Design and Research Methods

1. Population

The Center for Cancer and Blood Disorders (CCBD) at Children's Hospital Colorado sees approximately 240 new Oncology patients each year. Approximately 45% of these patients receive vincristine, a chemotherapy agent that is known to affect physical functioning. In addition, about 25% of these patients receive steroids, another medication known to affect physical functioning and quality of life. About half of the new patients each year are anticipated to fit the inclusion criteria. Therefore, we expect approximately 100 eligible subjects per year, with a 50% attrition rate, for a total sample size of 100 subjects over a two year period.

Enrollment for this study was reached in 2019. At this time, an additional 10 patients will be allowed to enroll on study to help supplement the data.

2. Eligibility Criteria

Inclusion

- Center for Cancer and Blood Disorders (CCBD) patient with Oncology or Neuro-oncology diagnosis
- No more than 2 previous sessions of CAT as an outpatient in the CCBD
- English speaking
- Receiving outpatient chemotherapy, biotherapy, or transfusions in the infusion center approximately weekly for at least 3 months.
- Ages 3 to 18 years

Exclusion

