- Hematology or other patients in the infusion center
- Patients who have previously received more than 2 sessions of CAT in the infusion center
- Non-English speaking patients

3. Study Design

A repeated measures design will be used with each patient serving as his/her own control.

Any Oncology patient in the CCBD who has not previously received more than two sessions of CAT in the outpatient unit and who will be receiving approximately weekly infusions of at least one hour in the infusion center will be identified by a research assistant. The study will be explained to the patient/family and informed consent will

be obtained by the principal investigator or the research assistant. A demographic form will be completed including the information of diagnosis, age, treatment, educational level of parents, zip code, prior experience with art, music, movement.

The intervention will consist of approximately weekly CAT in the infusion center during cancer therapy. The interventionist is a Master's prepared, licensed dance/movement therapist who is experienced in music and art therapies as well. The CAT includes dance/movement such as playing with a parachute, simple yoga breathing and postures, and work with physioballs. The music includes singing, listening to music, and playing instruments. The art consists of drawing, finger painting, working with clay. The CAT may occur in individual sessions in private infusion rooms, or in groups in the middle of the infusion center. The CAT is not only a distraction, but also a therapeutic process addressing the stressors of cancer and its treatment. The "dose" of CAT will be recorded (number and type of sessions) and will be factored into the analysis.

The subjects and/or parents will be tested with all instruments before the intervention, and approximately every 30 days for no less than 3 months and a maximum participation of 6 months. Treatment time points will be at least 30 days apart. Because some subjects are not scheduled to come into the clinic every 30 days for SOC appointments, they are unable to complete 3 sessions of CAT in a 3 month time period. For those subjects who are scheduled to come into clinic every 1-2 months for SOC appointments, study participation may take up to 6 months. This 6 month time period would allow for the completion of 4 different time points of CAT.

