We expect to recruit 100 patients, we also expect patients will be equally distributed in the following 3 categories: receiving low (0-3), intermediate (4-6) and high (7+) CAT sessions due to the nature of each patient's random visits. Power analysis was done based on pair-wise T-Test with these assumptions for simplicity. With 33 patients in each group, assuming 80% power and 0.017 significance level of alpha after Bonferroni ad justification of multiple comparisons, we will observe a minimum effect size of 0.813. This is to say that 80% of the Peds QL scores in the lower session CAT group will be below the average of scores in the higher session CAT group. Thus, what we would expect to see in the positive dose-response relationship.

We will also conduct subgroup analysis by age group if the sample size is large enough since Peds QL is designed by age group.

F. Summarize Knowledge to be Gained

Integrative and holistic therapies are being used throughout healthcare. We know that families are using alternative therapies without rigorous evidence documenting their worth. We therefore strive to build a body of literature showing evidence that CAT helps children with cancer feel better.

G. Appendices

1. PedsQL
2. Resilience Scale
3. Faces Scale
4. Inclinator information
5. Patient/Family Survey

H. References:

- Bhat SR, et al. (2005) Profile of daily life in children with brain tumors: an assessment of health-related quality of life.[see comment]. *J Clin Oncol*, 23, 5493-5500.

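### The only power statement assumes an equal split over three CAT session bands; no attendance data support the split, and no period for counting sessions is stated

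*Combined protocol and SAP*

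**What the plan says.** Section IV.E (Data Analysis Plan) expects 100 patients and three dose bands: low (0-3 sessions), intermediate (4-6) and high (7+). On how patients will fall into them it says "we also expect patients will be equally distributed in the following 3 categories", and the only reason offered is "due to the nature of each patient's random visits". It then states "With 33 patients in each group, assuming 80% power and 0.017 significance level of alpha", which gives a minimum effect size of 0.813. The method is described plainly: "Power analysis was done based on pair-wise T-Test with these assumptions for simplicity". No other power statement appears, and the plan says that it expects a positive dose-response relationship.

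Other sections bear on the split:

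- IV.B.2 (Eligibility Criteria) requires treatment "in the infusion center approximately weekly for at least 3 months".
- IV.B.3 (Study Design) says "The intervention will consist of approximately weekly CAT in the infusion center during cancer therapy".
- IV.B.3 also describes children who attend only every 1-2 months, of whom it says "they are unable to complete 3 sessions of CAT in a 3 month time period". Their participation may run to 6 months.
- IV.B.3 states that the number and type of sessions will be recorded and used in the analysis.
- IV.E sets the primary outcome, PedsQL, at about 3 months and adjusts all analyses for baseline.
- IV.B.1 (Population) says "Enrollment for this study was reached in 2019", with 10 further patients allowed.

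**The concern.** The bands are not randomised groups. Their sizes depend on how often children come and how often they take part, and neither the pilot summary nor the population section reports sessions per patient. Roughly weekly opportunities for 3 months make about 13, so a child who attends as planned passes 7 well before the primary assessment. Whether the lower bands fill depends on uptake and on how many children follow the sparser schedule, and the plan gives neither.

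The counting period is also open. Participation lasts 3 to 6 months and differs between patients, while the primary outcome is at about 3 months. A session total without an end date is not a defined exposure.

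There is no control arm, so this is the only comparison between levels of CAT exposure. If the low band is small, a null result for it says little. If the low band is mostly children on the sparser schedule, a positive result may reflect schedule rather than CAT.

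**Working it through.** **Inputs.** From IV.E: N = 100, 33 per band, alpha 0.017 (0.05/3 = 0.0167, rounded), power 80%, effect 0.813 SD. Sidedness is not stated; two-sided reproduces the figure. From IV.B.2 and IV.B.3: about 13 weekly opportunities in 3 months. Every split, uptake rate and correlation below is an assumption, because the documents give none.

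**1. The plan's own figure.** Two-sample t-test with noncentrality δ = d / √(1/n₁ + 1/n₂) and n₁ + n₂ − 2 degrees of freedom. For 33 v 33, δ = 0.813 / √(2/33) = 0.813 / 0.2462 = 3.302. The critical value on 64 df is 2.451, and power is 80.0%. There is no arithmetic error.

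**2. Other splits of 100, same formula.** Order: low v intermediate / low v high / intermediate v high. For an assumed baseline correlation of 0.5, the effect is divided by √(1 − 0.5²) = 0.866 and one df is removed.

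| Split | Power at 0.813, unadjusted | Detectable at 80%, unadjusted (SD) | Power, correlation 0.5 |
|---|---|---|---|
| 30/35/35 | 79/79/83% | 0.822/0.822/0.788 | 90/90/93% |
| 20/40/40 | 70/70/88% | 0.907/0.907/0.735 | 83/83/96% |
| 5/45/50 | 24/24/93% | 1.569/1.556/0.674 | 32/33/98% |

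Small departures from thirds cost little; strongly uneven splits cost a lot.

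**3. Which splits are plausible.**

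- *One common uptake rate.* With sessions binomial(13, p), the split is 42/52/6 at p = 0.3, 17/60/23 at 0.4 and 5/45/50 at 0.5. The 5/45/50 row therefore assumes that every child has the same rate.
- *Uptake varying among weekly children.* A beta-binomial with mean 0.41 and SD 0.21 gives about 32/32/36, with no infrequent attenders at all.
- *Two schedules.* Take 30% of children with 2 visits by 3 months, half attended, and 70% weekly at uptake 0.5. The low band is 0.30 + 0.70 × 0.046 = 33%, and the split is 33/32/35. Here 30/33.2 = 90% of the low band is the infrequent schedule.

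Near-equal bands can thus arise with or without a link between dose and schedule.

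**4. A trend on session count.** Slope = 0.813 / (mean sessions in 7+ minus mean in 0-3), and noncentrality = slope × SD of sessions × √100 / residual SD. At p = 0.5 the band means are 2.72 and 7.97, so the slope is 0.813/5.25 = 0.155. The session SD is √(13 × 0.25) = 1.803 and noncentrality is 0.155 × 1.803 × 10 = 2.79. Power at two-sided 0.05 is 79%.

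| Uptake | Trend, 0.05 | Trend, 0.017 | Low v high bands, 0.017 |
|---|---|---|---|
| 0.3 | 75% | 60% | 29% |
| 0.4 | 81% | 66% | 52% |
| 0.5 | 79% | 64% | 22% |

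These are unadjusted. With correlation 0.5 the 0.05 trend has 86/90/89%. At uptake 0.7 it has 54% (66% with correlation 0.5), because few children then have low counts. In the two-schedule case at 0.017, the trend has 86% against 81% for low v high.

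**5. The price of schedule.** In the two-schedule case, adding schedule as a covariate lowers the power of the 0.05 trend from 94% to 45% unadjusted, and from 98% to 57% with correlation 0.5. Leaving it out has its own cost. With no dose effect, correlation 0.5, and schedules assumed to differ by 0.3 or 0.5 SD, simulation finds the trend without schedule significant in 25.5% or 58.9% of runs. With schedule included, the rate is 4.8% at 0.5 SD.

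**The case against.** The best defence is that the plan may well be right about the split. Its stated reason is that visits vary from child to child, and varying uptake among weekly children alone can give nearly equal bands. That stands: no passage shows the split to be unequal. It also disposes of a tempting stronger reading, that near-equal bands must mean dose is confounded with visit schedule. Confounding is possible if both schedules are represented, but it does not follow.

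A reader might also infer that the missing counting period by itself moves the split a long way. The documents do not support that. In the two-schedule example, holding the infrequent children at 50% uptake over 4 visits in 6 months, and leaving the weekly children unchanged, gives 31/34/35 instead of 33/32/35. The 3-month endpoint is the natural period; the gap is that the plan does not say so.

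It is fair, too, that the calculation is labelled a simplification, that dose is to enter the analysis, that the covariate list is open, and that baseline adjustment may recover power. None of this supplies an attendance figure or a defined dose-response test. A null dose result could still be read from a confidence interval without a restated power figure, which is why the interval is part of the remedy.

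Finally, a trend at 0.05 owes part of its advantage to the looser alpha. But unadjusted it beats the low v high comparison at 0.017 as well, in every case tabulated.

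**Conclusion.** The point holds as an unsupported assumption and an undefined exposure, not as an error of calculation. The 80% at 0.813 SD applies to equal thirds only. Under the assumed splits, power for comparisons with the low band runs from 79%, which is immaterial, to 24%, which would make them uninformative. The plan does not show which applies. The lowest figure rests on a single common uptake rate.

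A reader might infer that the trial's primary analysis is underpowered. It is not touched: each patient is his or her own control in that comparison, and the bands play no part in it. With enrollment reached apart from the 10 additional patients, the matter concerns the analysis and reading of dose-response, not recruitment. It is worth correcting because a better test of the plan's stated expectation is available from data already being recorded.

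Separately, the weekly eligibility criterion in IV.B.2 and the account in IV.B.3 of children attending every 1-2 months conflict and must be reconciled.

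**What to change.** 1. Define dose as the number of sessions received up to the 3-month assessment.
2. Make the dose-response test one baseline-adjusted linear trend on that number, two-sided 0.05, reported with its confidence interval. Keep the three bands as description.
3. Replace equal thirds with the recorded session distribution and restate the detectable effect. This needs counts, not outcomes.
4. Tabulate sessions by visit schedule. If both schedules occur, report the trend with and without schedule as a covariate, side by side, and do not read the trend without schedule as causal.
5. Reconcile the eligibility and study-design passages on visit frequency.
6. Date the change, and label it post hoc if dose results have already been seen.

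The cost is wording, one table and one extra model, from session counts already recorded and visit dates; no patients are added. The trend assumes rough linearity, part of its power gain comes from being a single test at 0.05, and adjusting for schedule can cost substantial power.

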The testing will take place in an exam room after vital signs have been completed upon intake to the clinic. The trained research assistant, trained RN, or PI will administer the questionnaires. The PedsQL includes a subject report (ages 5 and over) and a parent report. The Resilience Scale is a self-report and will be used for ages 12 and over. The Faces Scale will use parent report for ages less than 5 and self-report for ages 5 and over. In order to confirm consistency, the posture measure will be completed by the PI (nurse practitioner) or registered nurse on the study after training with the manual included with the inclinometer tool.

Off Study Criteria

1. Subject discontinues CAT
2. Unable to complete 4 time points in 6 months

C. Description, Risks and Justification of Procedures and Data Collection Tools

The anticipated risks include psychological distress incurred by completing the outcome measure questionnaires as well as the therapeutic process. This risk will be minimized by the presence of the Master's prepared, experienced dance/movement therapist. The patients' social workers through the clinic will be available during the intervention as well.

D. Potential Scientific Problems

Based on the pilot data, the anticipated scientific problem is slow accrual due to unforeseen events during the traumatic time of a new diagnosis in pediatric oncology. We are unable to randomize because CAT is standard of care for any patient in the infusion center and therefore we feel it is unethical to deny CAT to a control arm. Therefore, we will compare the subjects to themselves over time to look at longitudinal changes of CAT.

E. Data Analysis Plan

The primary outcome is Peds QL at approximately 3 months; secondary outcomes will be the Resilience Scale, Faces Scale, and postural measurement at approximately 3 months. A repeated measures analysis of variance will be used to analyze the primary and secondary outcomes. We will also use the repeated measures analysis of covariance with the addition of covariates, depending on their statistical significance, such as gender, age, cancer diagnosis, and previous exposure to arts/music/dance. All of the analysis will be adjusted for baseline measures.

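### Does the plan need a new power statement and a formal dose-response test because its 0.813 effect size is for session groups rather than for the within-child primary analysis?

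*Combined protocol and SAP*

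**What the plan says.** Section IV.B.3 (Study Design) sets a within-child design: "A repeated measures design will be used with each patient serving as his/her own control". It also says that the dose of CAT "will be recorded (number and type of sessions) and will be factored into the analysis". Section IV.E names PedsQL at about 3 months as the primary outcome and states: "A repeated measures analysis of variance will be used to analyze the primary and secondary outcomes". All analyses are adjusted for baseline. Covariates may be added according to their significance; the examples given do not include session number, and the list is not exhaustive.

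The power paragraph in IV.E takes a different comparison. It assumes that "we also expect patients will be equally distributed in the following 3 categories: receiving low (0-3), intermediate (4-6) and high (7+) CAT sessions", then says "Power analysis was done based on pair-wise T-Test with these assumptions for simplicity". The setting is "With 33 patients in each group, assuming 80% power and 0.017 significance level of alpha", after a Bonferroni correction, with a minimum effect size of 0.813. The plan interprets this as about 80% of "scores in the lower session CAT group will be below the average of scores in the higher session CAT group", and closes: "Thus, what we would expect to see in the positive dose-response relationship".

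**The concern.** Two things look wrong at first. The sample size appears to be justified for a test that is not the primary analysis. A reader could take 0.813 as the sensitivity of the repeated measures ANOVA, for which the plan gives no target change, SD, within-child correlation, alpha or power.

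Secondly, there is no control arm, so variation in session number is the only exposure contrast that might help separate CAT from the passage of time, although it is not randomised. The plan expects a dose-response but does not say which model term or contrast tests it, or what result would support it. If three pairwise p-values were used, an analyst could decide afterwards how many had to be significant. If session number were treated as an optional covariate, its inclusion could depend on its own p-value.

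**Working it through.** **1. The plan's own figure.** Inputs from IV.E: 33 per group, alpha 0.017, power 80%, effect 0.813. Two-sidedness is inferred, because only the two-sided test reproduces the figure.

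- Noncentrality = d × √(n/2) = 0.813 × √16.5 = 3.302, with 64 degrees of freedom and critical t = 2.451.
- Power from the noncentral t = 80.0%. The solved minimum effect is 0.8129.
- A one-sided test would give a minimum effect of 0.742, and a paired test on 33 children 0.588. So 0.813 is a two-sided comparison of two independent groups.
- The plan's verbal gloss also fits: Φ(0.813) = 0.79, or about 80%.

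**2. Sensitivity of the within-child comparison.** The documents give no SD or correlation. Simplify to baseline against 3 months, paired t, two-sided 0.05 (assumed), 80% power.

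- n = 100: minimum mean change = 0.283 SD of change (noncentrality 0.283 × √100 = 2.83, 99 degrees of freedom, power 80.0%).
- n = 110, with the 10 extra patients: 0.270.
- n = 50, a deliberately pessimistic case: 0.404.
- In baseline-SD units at n = 100, multiply by √(2(1 − r)): 0.335, 0.283 and 0.219 at assumed correlations r of 0.3, 0.5 and 0.7.

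The units differ from those of 0.813, so the two cannot be ranked without assuming r. At these values of r the within-child comparison detects a smaller difference than the one the plan powered.

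**3. Would one trend test be better than pairs?** Assume equal thirds, SD 1, and a rise of 0.813 from low to high in two equal steps of 0.4065, before baseline adjustment.

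- Adjacent pair at 0.017: 22%. Low-high pair: 80%.
- Three-group linear trend: its noncentrality is also 3.302, with 96 degrees of freedom. Power is 90% at alpha 0.05 and 81% at 0.017. Most of the advantage comes from doing one test instead of three.

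For non-linear or unbalanced cases, compare the trend at 0.05 with at least one of three pairs significant at 0.017. The 10/20/70 split is an assumption.

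| Pattern, effect 0.813 | Split | Trend | Any pair |
|---|---|---|---|
| Step at low threshold | 10/20/70 | 48% | 55% |
| Step at high threshold | 10/20/70 | 92% | 87% |
| Inverted U | equal thirds | 4% | 91% |

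**4. A session-count slope adjusted for baseline and time to assessment.** With equal thirds coded −1, 0, 1, the SD of dose is √(2/3) = 0.816, so the same linear effect is 0.4065 × 0.816 = 0.332 SD per SD of sessions. Noncentrality = 0.332 × √(99 × (1 − R²)), where R² is the assumed share of session variance explained by the other covariates. At two-sided 0.05, before any gain from baseline adjustment, power is 90%, 81% and 64% at R² of 0, 0.25 and 0.50. Children who attend every one to two months may be followed for up to 6 months (IV.B.3), so some correlation between sessions and time is plausible.

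**5. Standing of the dose question.** Aims a to e in section I do not include dose-response, and IV.E does not list it as a primary or secondary outcome. It appears as an expectation at the end of the power paragraph.

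**The case for a change.** The strongest case for a change is that disclosing a shortcut does not supply the missing figure. A primary analysis should carry its own detectable effect. In a study without controls, the one informative exposure contrast should have its test fixed in advance, and the amendment would cost only wording because session counts are already recorded.

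Part of this stands. The plan gives no sensitivity for its primary analysis and does not say in what form session number enters the model. A sentence on each would make it clearer.

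The rest does not carry. The misreading of 0.813 is forestalled in the same paragraph, which describes it as lower against higher session group. The pairwise tests are introduced only to simplify the power calculation, so rules counting significant pairs are not rules the plan proposes. The commitment to use dose is unconditional in IV.B.3, so selection by its own p-value is only a possibility. Nor is session count the only comparison between children: IV.E also has covariates and age-group analyses, although those do not separate CAT from time.

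A dose test at 0.05 beside the primary time effect would raise its own question of which result supports a conclusion. Equal thirds is itself uncertain, since near-weekly CAT points towards 7+ while the less frequent attenders point the other way. With 20/40/40, power at 0.813 for low against high falls to 69%. That qualifies the secondary contrast, not the primary analysis.

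**Conclusion.** No change is needed. The stated figure is arithmetically right, it is disclosed as a simplification, and it is described as what it is. The missing within-child figure hides no demonstrated weakness: about 0.28 SD of change is detectable at n = 100, assuming a paired comparison, two-sided 0.05 and 80% power. With enrolment already reached, apart from 10 supplementary patients, a restated power calculation would change neither the sample size nor any estimate.

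The unspecified dose term is a gap that an analyst would fill sensibly. The plan already provides baseline adjustment, an ANCOVA framework and a commitment to use session number. Entering it there and reporting its coefficient with a confidence interval, as exploratory and non-randomised, follows from what is written. Mandating a linear trend is not a plain gain: 81% v 80% at equal alpha under a linear effect, 4% v 91% under an inverted U, and 64% to 90% for the time-adjusted slope, depending on how far sessions and the other covariates overlap. These powers rest on assumed effect shapes, group splits and R², none of which the documents give.
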